Hypothesis 2: Relative to Health Education, participants randomized to receive Tele-Self CBT will have greater improvements in subjective sleep (per diary on sleep onset latency (SOL), wake after sleep onset (WASO), sleep efficiency (SE), and objective sleep (per actigraphy WASO, total sleep time (TST), and SE), fatigue, depression symptoms, and sleep QOL at 8 weeks. *Aim 3:* To inform future efforts, we will use qualitative research methods to examine nurse and clinic administrator perspectives on implementing and disseminating Tele-Self CBT.

[figure not shown]

Figure 1

C. Randomized Controlled Trial (Aims 1 and 2)

C.1 Study Design

The proposed study is a randomized controlled trial comparing Tele-Self CBT to Health Education Control for improved insomnia severity among treatment-seeking Veterans with Insomnia (Figure 1). In this 2-arm trial, 200 participants will be randomized in a 1:1 ratio to Tele-Self CBT or a Health Education Control condition. Veterans who are: a) prescribed sleep medications; b) diagnosed with insomnia; or c) referred for clinic based CBT (but not yet treated) will be identified using electronic health records (EHR) and telephone interviews. Outcomes will be assessed at 3 time points: baseline, 8 weeks, and 6 months after baseline. These time points were selected to assess the immediate (8 weeks) effects of Tele-Self CBT, and to determine if Tele-Self CBT results in sustained improvements (6 months). Participants in both arms will continue to receive usual medical care. Each assessment period involves a) 2 weeks of home-based sleep assessment (diary and actigraphy), and b) completion of self-report

questionnaires. Following completion of a home-based sleep assessment period, a questionnaire-based assessment will be conducted by phone by a research assistant blinded to treatment condition. Study participants will be asked to return actigraphy devices (as well as any paper forms) at the end of each assessment period via prelabeled UPS envelopes dropped off at a UPS location.

C.2 Study Population

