Substance Use/Abuse: We will define alcohol abuse as documentation in the medical record of current alcohol abuse. Those with the two most recent AUDIT-C administrations documented in the medical record and scored as negative will be eligible for the study. The AUDIT-C⁸⁸, a well-validated 3-item screener for alcohol abuse used in VA⁸⁹ and primary care settings⁹⁰, to screen out those who are actively abusing alcohol. We will use the clinical scoring criteria for men and women respectively. We will use a single item to screen out those engaged in recreational drug use⁹¹. This item was found to be highly sensitive (100%) and moderately specific (73.5%) for detecting those with a drug use disorder and had good sensitivity (81.8%) and specificity (72.5%) for laboratory-based evaluation of drug use⁹¹.

Table 3. Assessment Measures

	Items	Timing		
		BL	8 weeks	6 months
Background-EHR Data				
VA Sleep & Psychotropic Medications	n/a	•		
Medical Conditions	n/a	•		
Mental Health Conditions	n/a	•		
Background-Self Report				
Demographic Characteristics	18	•		
Medical Conditions	up to 16	•		
Primary Outcome				
Insomnia Symptom Severity: ISI	7	•	•	•
Secondary Outcomes				
Actigraphy (WASO, TST and SE)	n/a	•	•	•
Sleep Diary (SOL, WASO and SE)	8	•	•	•
Fatigue: Multidimensional Fatigue Inventory	20	•	•	•
Depression: PHQ-8	8	•	•	•
Chronotype: MEQ	19	•	•	•
Trauma-related Sleep Disturbances (PSQI Addendum)	10	•	•	•
International Physical Activity Questionnaire	11	•	•	•

Glasgow Sleep Impact Index	7	•	•	•
Insomnia Treatment Knowledge Questionnaire	10	•	•	•
Ask if participant has accessed CBTI Coach and/or Path to Better Sleep	2		•	•

Outcome Measures

Outcome measures will be collected by phone by the project's research assistant (RA) at baseline, 8 weeks, and 6 months. Copies of self-report outcome measures are listed below.

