Morningness-Eveningness Questionnaire: The Morningness-Eveningness Questionnaire (MEQ) was the first self-report measure developed for the assessment of chronotype and continues to be the most widely used measure for this purpose. The MEQ has established psychometric properties¹⁰¹. We will use an updated version of the MEQ¹⁰ having rephrased questions that better conform to contemporary language. In addition, the revised MEQ utilizes a discrete item response set in lieu of the original visual response scales, allowing respondents to calculate their own score. MEQ scores range from 16 to 86, with lower scores indicating greater eveningness and higher scores indicating greater morningness. Total scores are used to categorize respondents into 5 categories, as follows: definitely morning; moderately morning; neither type; moderately evening; and definitely evening.

Trauma-Associated Sleep Disturbances: The Pittsburgh Sleep Questionnaire Addendum will be used to assess PTSD-related sleep quality and has acceptable psychometric properties.

International Physical Activity Questionnaire: The International Physical Activity Questionnaire is an 11-item questionnaire that assesses the respondent's physical activity over the previous week. This measure been widely implemented and has been used in the Veteran population.

Glasgow Sleep Impact Index: We will be using a 7-item modified version of the Glasgow Sleep Impact Index that excludes questions meant for clinical use only. This index is the only measure available that is specifically designed to assess sleep-related quality of life impairment.

Insomnia Treatment Knowledge Questionnaire: The Insomnia Treatment Knowledge Questionnaire was developed for the pilot study and will be used to assess participant comprehension of treatment components. In the pilot study, participants in the intervention condition reported higher scores (better understanding of concepts) at post-intervention relative to those in the control condition.

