3-8	INTERVENTION ARM Interventionist calls with participant to support treatment engagement and adherence.	Intervention Adherence Questions	6 nurse contacts @ 20 mins/call
3-8	HEALTH EDUCATION ARM Interventionist calls with participant to ensure equivalent contact time across arms.		6 nurse contacts @ 20 mins/call

STUDY CONTACTS			
Week#	Purpose of Contact	Measures	Time Commitment/Contact Modality
9-10	8 WEEK ASSESSMENT o Participant calls IVR sleep diary system daily for 2 weeks o At end of 2 weeks, participant completes 8-week assessment questionnaires by phone	Adverse Events query Insomnia Severity Index (ISI) Multi-Dimensional Fatigue Inventory (MFI) Morning Eveningness Questionnaire PSQI addendum Glasgow Insomnia Index IPAQ short phone Insomnia Treatment Knowledge Questionnaire PHQ-8 COVID questions Sleep medication and Other Treatment for your Sleep Complaint Intervention arm only: Treatment Acceptability/use	5 minutes daily/IVR <50 minutes/telephone
27-28	6 MONTH ASSESSMENT o Participant calls IVR sleep diary system daily for 2 weeks o At end of 2 weeks, participant completes 6-month assessment questionnaires by phone	Adverse Events query Insomnia Severity Index (ISI) Multi-Dimensional Fatigue Inventory (MFI) Morning Eveningness Questionnaire PSQI addendum Glasgow Insomnia Index IPAQ short phone Insomnia Treatment Knowledge Questionnaire PHQ-8 COVID questions Sleep medication and Other Treatment for your Sleep Complaint	5 minutes daily/IVR <50 minutes/telephone

Study Interventions

Tele-Self CBTI: The nurse interventionists will make an introductory call and set up a weekly call appointment time. As noted above, Tele-Self CBTI is comprised of two treatment components: 1) Self-management via our workbook entitled, “Improve your Sleep: A Self-Guided Approach for Veterans with Insomnia” with Session Guides; and 2) telephone-based nurse support. Our Tele-Self CBTI workbook includes the following typical CBTI treatment components: Sleep Restriction; Stimulus Control; Cognitive Therapy; Relaxation; and Sleep Hygiene Education⁹³. We will deliver Tele-Self CBTI across 6 weekly telephone contacts of 20 minutes or less. Table 5 describes the treatment modules and content of each telephone session, and the relative timing of treatment components.

Table 5. CBTI Treatment Components and Sessions

Module: Content	Veteran Workbook Readings	Nurse Support	Sleep Diary
Weekly		Weekly	Daily
1: Sleep Education; Sleep Diary Instructions	Session 1 (page 5)	X	X

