Coded data with direct identifiers removed (i.e., name, address, telephone numbers, SSN, DOB) will be placed at VINCI. We will be using REDCap a VA Intranet Web application

approved by VA and run by VA VIReC. The REDCap software is web-based but participants will be interviewed over the phone and data will be entered by study staff behind the VA's firewall. The data are housed on a VA Informatics & Computing Infrastructure (VINCI) Server. Data from the Actigraph device will be downloaded to our local server behind the VA firewall at `\v06.med.va.gov\HSDR\Insomnia_Self_CBTI_Trial_IRB_2147`. HSR&D servers are located in a secured area at [name]. All VA research personnel who have access to VHA records are instructed, in accordance with VA policy, on the requirements of Federal privacy and information laws and regulations, VA regulations and policies, and VHA policy. All study personnel who are VA employees working within the VA system have fulfilled all required HIPAA and other VA security and privacy policy training requirements and have agreed to follow guidelines pertaining to the protection of patient data. All research staff sign VA Rules of Behavior, and all study staff are up to date with VHA Privacy Policy Training and the VA Office of Cyber and Information Security Awareness Training Course. The data security and privacy procedures summarized in that course include logging off or locking the computer when walking away from it; no sharing of access codes, verify codes or passwords; not allowing anyone else to use the computer under one's password; and disposing of sensitive information using VA-approved methods (e.g., shredder bins). Access to study data will be removed for all study personnel when they are no longer part of the research team.

This is a minimal risk intervention for insomnia and we do not anticipate any safety issues related to the intervention. Patient activity will be monitored for Serious adverse events during the intervention period by intervention nurses.

Screening, baseline, and outcomes data will be collected via telephone at baseline, after the intervention (week 6) and at the 6-month follow-up. Suicidality will be assessed across the same timepoints, as part of the PHQ-8. The Suicide Safety plan will be implemented for patients endorsing suicidality during completion of the PHQ-8 at any point in study conduct, as discussed above.

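### The treatment-knowledge quiz in the blinded assistant's follow-up calls can partly reveal the arm, and the plan neither fixes its place in the call nor separates it from the other outcomes

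*Combined protocol and SAP*

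**What the plan says.** Section C.1 makes assessor blinding a design feature: after each home sleep assessment, "a questionnaire-based assessment will be conducted by phone by a research assistant blinded to treatment condition". Section C.8 (Outcome Measures) gives the task to one role at every visit: "Outcome measures will be collected by phone by the project's research assistant (RA) at baseline, 8 weeks, and 6 months". Section F.5 adds that "participants will be interviewed over the phone and data will be entered by study staff behind the VA's firewall", so the answers are spoken to a member of staff.

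Table 3 schedules the 10-item "Insomnia Treatment Knowledge Questionnaire" at baseline, 8 weeks and 6 months, among the secondary outcomes. Section C.8 describes it as a test of how well participants understand the treatment components, and reports from the pilot that "participants in the intervention condition reported higher scores (better understanding of concepts) at post-intervention relative to those in the control condition". It gives no mean, SD or overlap.

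In Table 4 the quiz stands directly before the PHQ-8 in both follow-up rows: "IPAQ short phone Insomnia Treatment Knowledge Questionnaire PHQ-8 COVID questions". The ISI, MFI and Glasgow index stand earlier in those rows. Table 3 puts the PHQ-8 ahead of the quiz.

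The description of the control condition bars sleep content from the control calls. No section fixes the order of the call, gives the quiz to someone else, or asks the assistant to record a guess of the arm.

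**The concern.** One arm is taught sleep restriction, stimulus control and the other CBTI components. The other arm is deliberately taught nothing about sleep. A quiz on those components is then put to both arms by the person who is meant not to know the arm. The leak is in the answers, not in the presence of the quiz, so giving it to everyone does not close it.

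Two sets of outcomes could be affected. Within a visit, any questionnaire asked after the quiz is exposed; on the Table 4 listing that means the PHQ-8, which serves the depression outcome of Hypothesis 2. Between visits, whatever the assistant learned at 8 weeks precedes the whole 6-month interview, which the plan uses to judge whether improvement is sustained and for which the model in Section E.2 carries its own treatment term. The stake is interviewer influence: how questions are read, probed and coded by someone with a view on which arm is speaking.

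**Working it through.** The plan states no figure on this point, so there is nothing to reproduce. The check compares the listings and adds one illustration.

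**1. Does the quiz come before other outcomes in the same visit?**

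| Interview outcome | Table 3, relative to the quiz | Table 4 (8 weeks and 6 months), relative to the quiz |
|---|---|---|
| ISI | before | before |
| MFI | before | before |
| Glasgow index | before | before |
| PHQ-8 | before | directly after |

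The two tables disagree only on the PHQ-8 among these four. Neither is called an order of administration. They also reverse the Glasgow and physical-activity questionnaires, and the baseline row of Table 4 omits the PHQ-8 that Table 3 schedules at baseline. So the within-visit exposure of the PHQ-8 is conditional on Table 4 being the call order. The 8-week ISI, the primary outcome, precedes the quiz in both listings, but no rule guarantees this.

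**2. Does the 8-week quiz come before the 6-month outcomes?** In time, yes: Table 4 puts the 8-week assessment at weeks 9–10 and the 6-month assessment at weeks 27–28. The route needs the same assistant to take both calls and to retain an impression over 27 − 10 = 17 weeks or more. Section C.8 speaks of one assistant; Section E refers to research assistants in the plural.

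**3. Which outcomes bypass the assistant's interview?** Diary SOL, WASO and SE come by IVR keypad (or the paper backup). Actigraphy WASO, TST and SE come from a device and a scoring algorithm. Neither group is exposed by this route.

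**4. How much could one score reveal?** Assume 1:1 allocation and normal scores with equal variance in the two arms, with means d SD apart. The best rule guesses the treated arm above the midpoint, and is right with probability Φ(d/2).

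| Assumed d | Φ(d/2) | Correct guesses |
|---|---|---|
| 0 | Φ(0) | 50% |
| 0.2 | Φ(0.1) | 54% |
| 0.5 | Φ(0.25) | 60% |
| 1.0 | Φ(0.5) | 69% |
| 2.0 | Φ(1.0) | 84% |

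The plan does not give d. These are upper values for each d, because they suppose an assistant who totals the score and knows the best cut-off.

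**5. Are there other leaks in the same contacts?** Yes, and they are more direct. Table 4 lists a treatment acceptability item for the intervention arm only at 8 weeks. Section C.8 (Covariate and Other Measures) says that the question on other sleep treatment goes to Tele-Self participants at both follow-ups, whereas Table 4 lists it without an arm restriction. If the assistant asks either item of one arm only, the assistant must know the arm.

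**The case against.** A reader might infer that the PHQ-8 and all 6-month outcomes are simply not taken blind. The documents do not support that. The pilot sentence reports a group difference of unstated size, which means partial leakage, not loss of blinding. The PHQ-8 sequence depends on reading Table 4 as a script, and Table 3 has the opposite order. The 6-month route needs the same assistant and a memory lasting months in a 200-person trial. Diary and actigraphy outcomes do not pass through the interview at all. These objections stand, and they set the limits of the point.

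It can also be said that any outcome that responds to treatment hints at the arm. Section E.3 sizes the trial on an ISI effect of 0.5, and the formula above gives 60% for a gap of that size too. This is fair for a small quiz gap. It is weaker for a quiz whose subject is the content taught to one arm and withheld from the other, and the ISI has to be in the call while the quiz does not.

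Finally, participants are told their arm and self-report every scale, so a blinded assistant cannot remove reporting bias. That stands and keeps the point minor. It does not make assessor blinding worthless, since the plan chose it to limit interviewer influence.

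**Conclusion.** The point holds as a risk of partial unblinding, of unknown size, to a stated design feature for which no safeguard is described. Conditional on Table 4 being the call order, it touches the PHQ-8 at both follow-ups. Conditional on the same assistant calling again, it touches the 6-month ISI, MFI, PHQ-8 and Glasgow index. If the listed order is followed, this route does not reach the primary 8-week ISI. The guess rates of 60% to 84% rest on assumed gaps of 0.5 to 2 SD and an ideal guesser; they are not estimates for this trial, and no bias in any outcome can be computed from the documents. This is a low-priority improvement, worth making because it costs almost nothing.

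**What to change.** - **Minimum:** in Table 4 and the call script, state the order of administration and give the quiz only after the ISI, MFI, PHQ-8, Glasgow index and every other interview outcome for that visit are entered. This is a text change. It protects that visit but not the 6-month interview if the same assistant calls again.
- **To protect 6 months as well:** take the quiz out of the assistant's call at 8 weeks and 6 months, together with the intervention-only acceptability item and the other-treatment question. Put them on the existing IVR line, or give them to the study coordinator, who already tells participants their arm, after the assistant's outcomes are entered. Moving the quiz alone would leave the more direct leaks in place.
- **Reconcile** Section C.8 and Table 4 on whether the other-treatment question goes to one arm or both.
- **Optional:** have the assistant record a guess of the arm at the end of each follow-up call, so that the leak can be reported.

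The cost is one short extra contact per follow-up, or some missing quiz scores. With the coordinator, a measure listed among the secondary outcomes would be collected by someone who knows the arm, so IVR is preferable, provided the quiz items can be answered by keypad.

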Wrist Actigraphy: We will use Actiwatch® (Respironics, Inc.) wristwatch style actigraphy watches for collecting objective sleep data as used in several prior studies. Actiwatches contain a calibrated accelerometer that samples, digitizes, and stores movement activity. When interfaced with a computer and Actiware software at the VA research site, a scoring algorithm provides estimates of various sleep parameters. Wrist actigraphy is recommended for assessing treatment response in adults with insomnia following intervention⁹⁶. The Actiwatch Spectrum Plus device is proposed and includes sensors for light and “off the wrist” which increase scoring accuracy. We will average data across each two-week assessment period to determine actigraphy-based WASO, Total Sleep Time (TST) and SE.

Instructions for Home Data Collections: The cover letters and instructions regarding use of the Actiwatch and Sleep Diary and timelines for the study will be provided to each patient with each delivery of the Actiwatch device.

Daytime Consequences of Insomnia: As recommended for insomnia research⁹⁶, we will assess fatigue, mood, and quality of life to evaluate the impact of Tele-Self CBTI on adverse

daytime consequences of insomnia. The Multidimensional Fatigue Inventory (MFI)¹⁰⁰ is a 20-item measure wherein the responder indicates, using a 5-point Likert scale, the extent to which each statement applies to their situation over the previous day). The MFI assesses 5 dimensions of fatigue, including: general fatigue; mental fatigue; physical fatigue; reduced activity; and reduced motivation. The PHQ-8 described above, will be used as our depression measure.

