E.1 Data Summary (Aims 1 & 2): Descriptive statistics, including graphical displays, will be used to summarize all study variables, both overall and by intervention group. Evidence of imbalance in baseline characteristics will be noted and discussed as to whether they are clinically significant. As recommended by Committee for Proprietary Medicinal Products¹⁰⁸ guidelines, we will consider sensitivity analyses adjusting for these baseline characteristics to ensure that an observed intervention effect is not due to baseline imbalance. Trajectory plots and frequency distributions will be used to explore longitudinal outcomes. We do not anticipate substantial deviations from symmetric, normal distributions for the study outcome variables. Additionally, correlation patterns over time, both overall and by intervention group, will be examined via scatter plots. The main conclusions drawn from this trial will be based on the pre-specified primary and secondary hypotheses outlined below and will be tested with two-sided p-values at the standard 0.05 level. All statistical analyses will be performed using the SAS software package (Cary, NC); the Durham HSR&D Center of Innovation maintains the current SAS release on the Durham VA hospital servers.

E.2 Intent to Treat Analyses (Aims 1 & 2): All primary and secondary analyses focus on the effect of the intervention compared to control. We, therefore, plan to use the intent-to-treat assumption for all analyses; participants will be analyzed as part of the group to which they are randomized, regardless of intervention adherence.

Hypothesis 1: Relative to Health Education, participants randomized to receive Tele-Self CBT will have greater improvements in insomnia severity, as measured by the Insomnia Severity Index (ISI), at 8 weeks. The ISI is a continuous measure wherein lower scores indicate less severe insomnia symptoms. A general linear model will be used to estimate changes in ISI over time and test the primary hypothesis. Because of the small number of time points, we will apply

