an unstructured covariance matrix to take into account the within-patient correlation between repeated measures over time. The predictors in the model will include a dummy coded time effect and an indicator variable for Tele-Self CBT interacting with the time effect. The mean structure of the model will have the form: $Y = \beta_0 + \beta_1 * 6\text{wk} + \beta_2 * (\text{month6}) + \beta_3 * (\text{Tele-Self CBT1} * 6\text{wk}) + \beta_4 * (\text{Tele-Self CBT1} * \text{month6}) + \beta_5 * (\text{age}) + \beta_6 * (\text{baseline ISI})$, and model parameters will be estimated using the SAS procedure MIXED (Cary, NC). Note that this model is a constrained intercept model, which assumes a common baseline mean¹⁰⁹. We will formally evaluate the intervention effect by testing that β_3 differs from zero and report the mean difference and corresponding 95% confidence interval. A mean difference significantly less than zero provides evidence that Tele-Self CBT patients have greater improvements in ISI at 8 weeks. The model will also include centered, stratification variables of age ($\leq 50/ > 50$ years), baseline ISI ($\leq 20/ > 20$), *mental health disorder status (presence/absence)*, *psychotropic medication (use/non-use)* and *sleep medication (use/non-use)* as recommended in the CPMP guidelines¹⁰⁸.

Hypothesis 2: Relative to Health Education, participants randomized to receive Tele-Self CBT1 will have greater improvements in subjective sleep (per diary SOL, WASO, and SE), objective sleep (per actigraphy WASO, TST, and SE), fatigue, depression symptoms, and QOL at 8 weeks. As described above, sleep parameters (both diary and actigraphy) are recorded daily during each of the three 2-week assessment periods. Daily values will be averaged across each 2-week period, resulting in three repeated continuous outcomes for each of the sleep parameters, including baseline, 8 weeks, and 6 months. Treatment group differences at 8 weeks and 6 months for these subjective and objective sleep measures will be tested via the same general linear model as specified above for the primary hypothesis. Similarly, the fatigue, depression symptoms and QOL outcomes will also be analyzed with a general linear model as specified above for the primary hypothesis. Again, PROC MIXED will be used to estimate and test the appropriate model parameters, and the mean difference and corresponding 95% confidence intervals will be reported.

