E.3 Sample Size Considerations (Aims 1 & 2): Our sample size estimates are based on the Hypothesis 1 primary outcome – Insomnia Severity Index. Because this is a longitudinal study with repeated measurements on each subject, mean change is estimated with increased precision. In sample size calculations, the increase in precision can take into account the correlation between repeated measures. With Tele-Self CBT1, we anticipate seeing smaller effects than might be seen with in-person CBT1. Additionally, our comparison group receives more than usual care, again leading to smaller effects. In a recent meta-analysis, the effect of CBT1 on ISI yielded large Hedge's g effect sizes of 0.98. Conservatively, we then base our sample size estimates on an effect size of 0.5; this translates into a relative mean improvement on the ISI of at least 2.8. Assuming a baseline SD of 5.8, a repeated-measures correlation of 0.6 (both quantities estimated from previous studies^[37,52,54,114]), and a type-I error of 5%, we will need to have 73 patients in each arm to detect a relative mean improvement of 3 on the ISI with 90% power. To account for dropout and possible deviations from our assumptions, we plan to enroll and randomize 100 patients in each arm (total sample size n=200). With this sample size, we will also have adequate power to examine our secondary outcomes. For example, previous studies of SE show a baseline SD of 12.5 and repeated-measures correlation of 0.7. With our projected sample size, we will have 90% power to detect a relative improvement in SE of at least 6.2. The repeated-measures design option in PASS¹¹⁵ was used for all calculations.

E.4 Data Analysis (Aim 3)

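### Hypothesis 2 feeds the trial's main conclusions through nine 8-week outcomes, each tested at 0.05, with no multiplicity control, no gate on the ISI result and no rule for when it is supported.

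*Combined protocol and SAP*

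**What the plan says.** E.1 (Data Summary, Aims 1 & 2) sets the basis for inference: "The main conclusions drawn from this trial will be based on the pre-specified primary and secondary hypotheses outlined below". These hypotheses "will be tested with two-sided p-values at the standard 0.05 level".

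Under E.2, Hypothesis 1 comes down to one coefficient for one outcome at one visit: "We will formally evaluate the intervention effect by testing that β_3 differs from zero". Hypothesis 2 is a single sentence that expects "greater improvements in subjective sleep (per diary SOL, WASO, and SE" from the diary, then "objective sleep (per actigraphy WASO, TST, and SE), fatigue, depression symptoms, and QOL at 8 weeks". That makes nine outcomes: three diary, three actigraphy, fatigue, depression and sleep quality of life. Each is analysed with the primary model, and mean differences with 95% confidence intervals are to be reported.

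Although Hypothesis 2 names only 8 weeks, E.2 adds a second visit for the sleep measures: "Treatment group differences at 8 weeks and 6 months for these subjective and objective sleep measures will be tested".

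The plan contains no multiplicity adjustment, no testing order, no condition on the ISI result, and no statement of whether one, some or all of the nine outcomes must be significant. The fatigue endpoint is also open. Section C.8 says "The MFI assesses 5 dimensions of fatigue" but does not name the score that Hypothesis 2 uses.

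**The concern.** Unadjusted secondary tests are common and usually harmless when the plan makes clear that only the primary endpoint carries the conclusion. E.1 says otherwise: it names the secondary hypotheses, with the primary, as the source of the main conclusions. As written, a null ISI result with one nominally significant secondary outcome could still be presented as a main finding that Tele-Self CBTI improves sleep or daytime function.

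Because no success rule is stated, the choice between any, several and all of the nine can be made after the results are known. The error attached to Hypothesis 2 depends almost entirely on that choice.

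**Working it through.** **Inputs from the plan.** Two-sided 0.05 per test (E.1). Nine 8-week outcomes (E.2). ISI: SD 5.8, repeated-measures correlation 0.6, 73 per arm, 90% power. Sleep efficiency (SE): SD 12.5, correlation 0.7, difference 6.2 at 90% power. Enrolment of 100 per arm (all E.3).

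**Assumed.** The correlation among the nine test statistics is not in the plan, so a range is shown. All error rates below suppose no effect on any of the nine outcomes.

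**1. The plan's own sample size.** E.3 says of its effect size that "this translates into a relative mean improvement on the ISI of at least 2.8". With a change-score variance of 5.8² × 2(1 − 0.6) = 26.91, n = 2 × (1.960 + 1.282)² × 26.91 / 2.8² = 72.1, so 73 per arm. This matches the plan. (The difference of 3 printed beside the 73 would need only 63.) The plan's arithmetic is therefore change-score based, at 0.05, for the ISI alone. It makes no allowance for multiple tests.

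**2. At least one false positive among nine.**
- Either direction, independent: 1 − 0.95⁹ = 37.0%.
- Benefit only, independent: 1 − 0.975⁹ = 20.4%.
- Equally correlated normal statistics, by simulation (1,000,000 draws):

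| Correlation (assumed) | Any significant, either direction | Any significant, favouring Tele-Self CBTI |
|---|---|---|
| 0 | 37% | 20% |
| 0.3 | 33% | 17% |
| 0.5 | 27% | 13.5% |
| 0.7 | 20% | 10% |

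The nominal figures for one test are 5% and 2.5%. The nine outcomes overlap (WASO and SE come from the same nights), so independence is the upper end of the range.

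**3. How much the missing rule matters.** If all nine must be significant in the favourable direction, the same simulation gives about 0.01% at correlation 0.5, 0.1% at 0.7 and 0.6% at 0.9. The unstated rule therefore moves the error from near zero to as much as 37%.

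**4. The fatigue score.** If all five dimensions were tested, there would be 8 + 5 = 13 tests at 8 weeks, and 1 − 0.95¹³ = 48.7% if independent.

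**5. Cost of adjustment.** Holm's strictest step uses 0.05/9 = 0.0056 (critical value 2.773). The SE difference detectable with 90% power is (2.773 + 1.282) × s × √(2/n). Here s = 12.5 × √(1 − 0.49) = 8.93 with baseline adjustment, or 12.5 × √(2 × 0.3) = 9.68 for a change score.

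| Per arm | Variance basis | Detectable SE difference | Power for 6.2 |
|---|---|---|---|
| 73 | Baseline-adjusted | 6.0 | 92% |
| 73 | Change score | 6.5 | 86% |
| 100 | Baseline-adjusted | 5.1 | 98% |
| 100 | Change score | 5.6 | 96% |

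The 6.2 is itself a weak benchmark. At 0.05 the change-score calculation gives 5.2 with 73 per arm and 4.4 with 100. It is close to what 0.01 with 73 per arm would give (6.18), but no such level is stated, so this is not evidence of a planned adjustment.

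**The case against.** The best defence is that the plan does rank its outcomes. Table 3 separates primary from secondary, C.8 makes the ISI the primary measure, E.3 sizes the trial on Hypothesis 1 alone, and the formal-evaluation sentence sits under Hypothesis 1. The E.1 sentence follows text on sensitivity analyses and exploratory plots, so it may be meant only to set pre-specified hypotheses apart from those. Hypothesis 2 joins its outcomes with *and*; read literally, it needs all nine. All nine are named in advance, share one model and are reported with intervals, which limits selective reporting.

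Much of this stands. The ranking is real, the primary test's 5% error is untouched, and an any-one-of-nine rule is not written down. But no sentence makes the secondary hypotheses merely supportive, and E.1 names them as a basis for the main conclusions. The all-nine reading is no more explicit than the any-one reading.

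Two stronger readings should be resisted. A reader might infer that a false secondary claim is probable; for the nine 8-week tests every figure is below one half, and a false claim of benefit reaches 20% at most. A reader might also count nine outcomes at two visits and quote 1 − 0.95¹⁸ = 60%. E.2 explicitly states 6-month testing only for the six sleep measures, which gives 15 tests (1 − 0.95¹⁵ = 53.7% if independent). Treating one outcome's two visits as independent also conflicts with the repeated-measures correlations of 0.6 and 0.7 in E.3.

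**Conclusion.** The concern holds for secondary claims only. E.1 lets Hypothesis 2 support a main conclusion with its error rate uncontrolled and its success rule undefined. The error is up to 37% for any false positive and up to 20% for a false claim of benefit. Both figures rest on three assumptions: no effect on any of the nine outcomes, one fatigue score, and any single significant result counting as support. Positive correlation lowers them, and an all-nine rule would bring them close to zero.

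This is more than missing detail, because E.1 states what the conclusions will rest on and at what level. It does not threaten the ISI analysis.

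**What to change.** - In E.1, state that the main conclusion rests on Hypothesis 1 (ISI at 8 weeks) and that Hypothesis 2 is supportive.
- Report Holm-adjusted p-values for the nine named 8-week outcomes beside the planned unadjusted estimates and 95% confidence intervals. Holm keeps the family-wise error at or below 5% whatever the correlation.
- Name one fatigue score in advance, so that the family is fixed at nine.
- Keep the planned 6-month comparisons, since C.1 includes that visit to judge sustained improvement. Label them supportive and outside the adjusted family.

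The change is a few sentences and one SAS step (PROC MULTTEST), and should be made before any comparison by arm is seen. The price is lower power for single secondary outcomes. At Holm's strictest step, 90% power for SE needs a difference of about 6.0 to 6.5 with 73 per arm, or 5.1 to 5.6 with 100, depending on the variance basis. Later Holm steps are less strict. The stated SE difference should also be re-derived with its significance level given.
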